Objective: Aim 1: Conduct a pilot RCT comparing AIR (n = 40) with sleep education (control condition; n = 40) for Veterans with OSA, insomnia, and PTSD. Hypothesis 1a: Veterans receiving AIR will demonstrate improved quality of life (WHOQOL-BREF; primary outcome) and functioning (FOSQ-10; secondary outcome) compared with control at post-treatment and follow-up assessments. **Hypothesis 1b**: Veterans receiving AIR will demonstrate greater reduction in symptoms of insomnia (ISI and actigraphy) and PTSD (CAPS-5), and greater adherence to PAP (device data capture) compared with control at post-treatment and follow-up.

Aim 2: Evaluate the feasibility and acceptability of AIR. Participants will complete a Feasibility and Acceptability Questionnaire (FAQ) and follow-up interview based on their questionnaire responses. Topics will include content of treatment as well as experience completing the treatment delivered via telehealth. Examination of treatment dropout and attendance at other PAP-related appointments will also be monitored to determine whether the treatment facilitated increased engagement in care. Hypothesis 2a: Veterans receiving AIR will report at least moderate agreement with items on the FAQ. Hypothesis 2b: There will be lower dropout in the AIR condition compared with control. Hypothesis 2c: There will be greater engagement in apnea care in the AIR condition compared with control

**Aim 3 (Exploratory): Evaluate moderators of treatment outcome.** I will evaluate the data for trends indicating potential moderators of treatment outcomes, such as sleep apnea severity or concurrent medication use.

Design: First, I will conduct a randomized controlled trial of AIR and a sleep education control condition. The primary outcome will be quality of life. Next, I will solicit Veteran feedback to assess the feasibility and acceptability of AIR and evaluate measures of engagement in care. Finally, I will identify moderators of treatment outcome, which may help target Veterans for whom the treatment needs further refinement.

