Clinical interview. Trained clinical interviewers will conduct the CAPS-5 interview to establish PTSD diagnosis and SCID-5 interview to establish insomnia diagnosis. This will take place over phone or video. The SCID-5 will also be used to rule out diagnostic exclusion criteria and establish comorbid mental health conditions for data analytic purposes. A brief medication interview will be conducted to obtain information about recent and current medication use. Interviews will be audio-recorded and reviewed by the Stress and Health Research Program's clinical assessment supervisor \*This is solely for research purposes.

Baseline prospective sleep data. Once eligibility is established, the Veteran will be shown how to complete a sleep diary. He or she will then record one week of baseline sleep data. Research staff will email the Veteran a link to enter sleep diary data via Qualtrics. The Veteran's PAP setup appointment (if needed) and treatment schedule will be planned. \*This is for research purposes; however, please note that completing a sleep diary is also part of routine care.

**Actigraphy.** The actigraph is a device worn on the risk to measure time asleep vs. awake. A subset of participants will be asked to wear the actigraph. The information will be used solely for research purposes. It is not part of the treatment.

**Baseline appointment**. The Veteran will complete pre-treatment measures. He or she will be randomized to either AIR or SE. \* Many of the pre-treatment measures are completed as part of routine care, but some are added for research purposes.

**Randomization procedure.** A block-randomization procedure will be used to assign participants to AIR or SE in a 1:1 ratio. Block sizes will be a random permutation of 4 and 6. Statistical consultant [REDACTED] will produce the computer-generated list. Each therapist will have his or her own randomization list. The randomization to treatment is for research purposes.

**Weekly assessment.** At the start of each treatment appointment, the Veteran will complete two self-report questionnaires assessing sleep (ISI and ESS). The Veteran's PAP adherence data and actigraphy data will also be downloaded or requested verbally. A copy of the Veteran's sleep diary will be obtained. At his or her final treatment appointment, the Veteran will be asked to complete a sleep diary to submit at the Post-Treatment

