Assessment appointment. In addition, at weeks 1, 3 and 5, the Veteran will complete the primary and secondary functioning outcome measures (WHOQOL-BREF and FOSQ-10.) \*Completion of ISI and ESS, sleep diary data, and PAP adherence are part of routine care and will also be used for research purposes. The additional WHOQOL-BREF AND FOSQ-10 at weeks 1, 3 and 5 are for research purposes.

**Post-Treatment Assessment.** One week following his or her final treatment appointment, the Veteran will attend the post-treatment assessment appointment via phone or video. He or she will turn in the sleep diary with data from the preceding week. He or she will turn in the actigraphy device. The Veteran will complete post-treatment questionnaires. A trained, blinded clinical interviewer will repeat the CAPS-5 interview (current symptoms only) and SCID-5 (insomnia portion only) and inquire about medication changes. The Veteran will complete a brief feedback interview about their treatment experience with study staff. The Veteran's PAP adherence data will be downloaded or provided verbally. \*This is for research purposes.

**3-Month Follow-Up Assessment.** Veterans will complete the 3-month follow-up questionnaires. PAP adherence data will be downloaded or provided verbally. If the Veteran's PAP device does not have a functional modem, the study team will arrange for the Veteran to provide their SD card for data download. The data will be uploaded to the appropriate clinical data monitoring system and the SD card will be returned to the Veteran. Veterans' charts will be checked to track PAP follow-up appointment attendance, if applicable. Veterans will be sent a sleep diary to complete the week prior to this appointment and will submit it at this appointment. \*This is for research purposes. However, review of PAP adherence data at 3-month follow-up is also part of routine care in the Sleep Clinic.

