**Dropout.** An important aspect of feasibility and acceptability is behavioral: whether Veterans attend and complete treatment. We will examine whether there are differences in completion between AIR and SE. If there is higher dropout in the AIR condition, we will need to make thoughtful adjustments to the protocol prior to the full-scale RCT proposal based on Veterans' feedback about treatment. We will also examine when dropout does occur. If most dropout should occur immediately after randomization (as has been our experience in previous trials), we will be less concerned about the acceptability of treatment than if most dropout occurs later once treatment is initiated. \*This is for research purposes. Engagement in follow-up care. Veterans with new PAP setups in the Sleep Clinic are scheduled for a return visit with a sleep technician or nurse practitioner approximately three months following receipt of PAP. This visit is important to ensure optimal treatment and address any barriers to adherence and follow-up care in the case of non-adherence. If PAP is not going to be used, other treatments may be indicated (such as oral appliance or surgery), but if the Veteran does not attend this appointment, he or she is lost to follow-up and will go untreated. We will assess for differences between AIR and SE in attending this follow-up appointment. This analysis will only be applicable to Veterans with new PAP

Statistical Analysis Plan: Baseline characteristics of both groups (demographic, diagnostic, and pre-treatment levels of outcome measures) will be described using appropriate summary statistics. We will examine the distributions of outcome measures for outliers and evaluate the need to transform data. Identification of potential outliers will prompt review of data to evaluate for data entry errors; analyses including and excluding

setups that occurred during this participation in this study. \*This is for research purposes.

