outliers will be conducted to evaluate influence on outcomes. Primary analyses will be unadjusted intent-to-treat analyses, with all subjects randomized to a treatment condition included. We will use linear mixed models, which are robust to data missing at random, to accommodate missing data due to dropout. Demographic and other baseline variables that show large group imbalances despite randomization will likewise be entered as covariates in a secondary sensitivity analysis, but will not be included in the primary analyses. Substantial differences in inferences supported by the primary and secondary analyses would indicate a potential problem of randomization failure, and would warrant caution in interpreting results of the primary analyses

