## Hypothesis Testing.

**Hypothesis 1a**: Veterans receiving AIR will demonstrate improved quality of life (WHOQOL-BREF; primary outcome) and functioning (FOSQ-10; secondary outcome) compared with control at post-treatment and follow-up assessments.

Analyses. The WHOQOL-BREF psychological domain score will be considered the primary outcome of the study, whereas the FOSQ-10 is a secondary measure of functioning. Both the WHOQOL-BREF and FOSQ-10 are administered at pre-treatment, week 3, week 5, post-treatment, and 3-month follow-up. Separate analyses will be conducted for each measure. A linear mixed model will be estimated for each score with subjects entered as a random effect and treatment group and time entered as fixed effects. Pre-treatment scores will be entered as a covariate, and time (week 3, week 5, post-treatment, and follow-up) will be entered as a categorical predictor to accommodate non-linear changes over time. The hypothesis will be tested by the significance of the group differences in baseline-adjusted post-treatment scores. The baseline-adjusted group difference at post-treatment will be divided by the standard deviation of baseline scores to calculate the standardized effect size. Durability of effects at 3 months will be tested by examining group differences in baseline-adjusted follow-up scores.

**Hypothesis 1b**: Veterans receiving AIR will demonstrate greater reduction in symptoms of insomnia (ISI and actigraphy) and PTSD (CAPS), and greater adherence to PAP (device data capture) compared with control at post-treatment and follow-up assessment.

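### The primary model excludes Veterans with no score from week 3 onward, although the plan says all randomized are included, and it leaves out the week-1 scores the protocol collects (minor)

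*Combined protocol and SAP*

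**What the plan says.** The opening of the Statistical Analysis Plan calls the primary analyses unadjusted intent-to-treat, "with all subjects randomized to a treatment condition included", and relies on linear mixed models under missing at random to deal with dropout.

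Under Hypothesis 1a the WHOQOL-BREF and FOSQ-10 "are administered at pre-treatment, week 3, week 5, post-treatment, and 3-month follow-up". The pre-treatment score is a covariate, and "time (week 3, week 5, post-treatment, and follow-up) will be entered as a categorical predictor to accommodate non-linear changes over time". The fixed effects named are treatment group and time; a group-by-time term is not mentioned.

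The Weekly assessment section gives a different schedule: "at weeks 1, 3 and 5, the Veteran will complete the primary and secondary functioning outcome measures". It also places the weekly questionnaires at the start of each appointment.

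On the timing of loss, the Dropout section says: "If most dropout should occur immediately after randomization (as has been our experience in previous trials"), acceptability would be less of a worry than with later dropout. No dropout rate is given. Neither imputation nor a rule for Veterans without a post-baseline score is described.

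**The concern.** A mixed model uses a subject only through that subject's outcome rows. Once the pre-treatment score is a covariate, a Veteran whose only scores are pre-treatment, or pre-treatment and week 1, has no row in the model as written. The stated analysis set and the stated model then describe different populations.

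Two things are at stake. The first is whether the reported population for the primary outcome is correct. The second is whether the appeal to missing at random holds. If early loss is related to the week-1 score and differs by arm, the variable that explains the loss has been observed but left out of the model. Loss that differs by arm is not far-fetched here, because Hypothesis 2b predicts lower dropout in AIR. Other models in the plan are not built this way: the ISI model has rows from session 1, and the CAPS model tests a group-by-time interaction on pre- and post-treatment scores, so pre-treatment is an outcome there.

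**Working it through.** The plan states no figure to reproduce: Hypothesis 1a gives no dropout rate, SD or detectable effect. The inputs from the documents are 40 Veterans per arm (Objective, Aim 1), 1:1 allocation, randomization at the baseline appointment, and the two outcome schedules above. Loss rates, correlations and the strength of the loss mechanism are assumptions.

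**Step 1. Who has an outcome row?**

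| Scores available | Model as written | Covariate model plus week-1 rows | Pre-treatment as an outcome row |
|---|---|---|---|
| Pre-treatment only | out | out | in |
| Pre-treatment and week 1 only | out | in | in |
| Stops treatment, answers post-treatment or follow-up | in | in | in |

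**Step 2. How many are excluded?** Excluded = 40 × (AIR rate) + 40 × (SE rate), where the rate is the share with no score from week 3 onward.

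- 5% and 15%: 40 × 0.05 + 40 × 0.15 = 2 + 6 = 8 of 80.
- 10% and 25%: 40 × 0.10 + 40 × 0.25 = 4 + 10 = 14 of 80.
- 20% in both arms: 80 × 0.80 = 64 analysed as written. Adding week-1 rows gives 72 if half of those lost leave after week 1, 80 if all do, and still 64 if none do. With pre-treatment as an outcome row, all 80 are in every case.

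**Step 3. What bias follows at post-treatment?** This was simulated with a large sample and no true effect. Pre-treatment, week-1 and post-treatment scores have SD 1 and a common within-subject correlation of 0.5 to 0.7. Loss before week 3 follows logit P(loss) = a(arm) − s × score, with s from 0.5 to 1.0 per SD and a(arm) set to give the rates in Step 2. Two estimates were compared:

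- As written: the group coefficient from regressing post-treatment on group and pre-treatment score among those retained.
- Using week 1: b(group) + b(week 1) × D, where the b's come from regressing post-treatment on group, pre-treatment and week 1 among those retained, and D is the baseline-adjusted week-1 group difference in everyone.

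| Loss depends on | Bias, as written | Bias, using week 1 |
|---|---|---|
| Week-1 score | about 0.01 to 0.03 SD | about 0.002 SD or less |
| Pre-treatment score only | within 0.002 SD of zero | within 0.002 SD of zero |

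**Step 4. Scale.** With a standard error of about 0.20 SD for the post-treatment difference, 0.01/0.20 = 5% and 0.03/0.20 = 15% of one standard error.

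**Step 5. Why group-by-time terms are needed if week 1 is added.** Suppose the effect is zero at week 1 and d at the other four times. A single group effect averaged equally over five times is then 4d/5 = 0.8d. Separate group-by-time terms keep the post-treatment contrast at d.

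**The case against.** The case against has several parts, and most of it stands.

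- A reader might infer that every Veteran who leaves treatment early is removed. The documents do not support that. Hypothesis 2b defines dropout as not completing six sessions, and the post-treatment assessment is by phone or video with a 3-month follow-up after it. A Veteran who answers either one keeps a row. However, the plan never says that those who stop treatment will still be assessed, and it times the post-treatment visit from the last treatment appointment.
- A reader might also infer that the sponsor forecasts heavy early dropout. The Dropout section makes a conditional remark that mentions past trials, and no rate is given.
- Nor can the remark about loss straight after randomization be combined with the week-1 bias argument. Veterans who leave before session 1 have no week-1 score, so week-1 data cannot help them. If their loss depends on pre-treatment score and arm, the covariate model already conditions on both and is essentially unbiased.
- For Veterans with only a pre-treatment score, changing the model barely alters the inference. At 40 per arm with 10% and 25% early loss (assumed correlations 0.55-0.65), the SD of the estimate was 0.209 with the covariate model and 0.208 with the constrained one. Precision lost through missing outcomes is not recovered.
- Week 1 may in effect be a second baseline, because the questionnaires come at the start of the appointment. That is a reason to use group-by-time terms. It does not explain why the two schedules disagree.
- A baseline covariate in a mixed model is standard practice, and this is a pilot. True, but the sentence about the analysis population still has to match the model.

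**Conclusion.** The point holds in a limited form and is minor. As written, the primary model does not include all randomized Veterans: anyone with no WHOQOL-BREF or FOSQ-10 score at week 3 or later is excluded from the analysis of that measure. The SAP schedule also contradicts the Weekly assessment section about week 1.

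Under the assumed loss of 5-10% in AIR and 15-25% in SE, 8 to 14 of 80 are excluded. The bias is about 0.01-0.03 SD, and only if loss depends on the week-1 score and differs by arm; using week 1 nearly removes it. If loss depends only on the pre-treatment score, the gain is a correctly stated population. The stronger conclusion, that the primary result would be materially biased or the missing-at-random argument fails in general, is not supported.

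**What to change.** - Reconcile the week-1 schedule between Weekly assessment and Hypothesis 1a.
- For the WHOQOL-BREF and FOSQ-10, fit a constrained longitudinal model with pre-treatment, week 1, week 3, week 5, post-treatment and follow-up as outcome rows, a common pre-treatment mean for the two arms, and group-by-time terms after it. The post-treatment and follow-up contrasts are read from those terms, so an early score possibly taken before any session content does not dilute them.
- Report by arm the number of Veterans with no post-baseline score.
- If the covariate model is kept, add the week-1 rows with group-by-time terms, and restate the analysis set as all randomized Veterans with at least one post-baseline score.

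The cost is SAP wording. No new data are needed, because the protocol already collects every score used.

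### A secondary model with covariates picked for observed imbalance is used as a test of randomization, which can cast unwarranted doubt on a sound primary result

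*Combined protocol and SAP*

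**What the plan says.** The Objective section sets the comparison as "AIR (n = 40) with sleep education (control condition; n = 40". Under Randomization procedure, blocks are used to "assign participants to AIR or SE in a 1:1 ratio". On the blocks and lists the plan says "Block sizes will be a random permutation of 4 and 6" and "Each therapist will have his or her own randomization list". Therapist is therefore the only stratification factor, and allocation is not balanced on any patient characteristic.

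The Statistical Analysis Plan paragraph then states: "Primary analyses will be unadjusted intent-to-treat analyses". On other covariates it says: "Demographic and other baseline variables that show large group imbalances despite randomization will likewise be entered as covariates in a secondary sensitivity analysis". It keeps these variables out of the primary analyses. A substantial difference between primary and secondary inferences "would indicate a potential problem of randomization failure" and is to prompt caution about the primary results.

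Under Hypothesis Testing, the model for the primary outcome (WHOQOL-BREF psychological domain) has one pre-specified baseline covariate: "Pre-treatment scores will be entered as a covariate". No other covariate is named in advance for adjustment. The plan does not say how large an imbalance is 'large' or what makes a difference in inference 'substantial', and no other section gives a different reading of such a difference.

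**The concern.** Randomization fails when the list is wrongly generated, concealment is broken, or participants do not receive the assignment on the list. A difference between two regression models shows none of these. With sound allocation, adjusted and unadjusted results can differ because a covariate is prognostic, because precision changes, or because a p-value lies close to the threshold. The type I error of the primary test already allows for chance imbalance.

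The plan's rule can mislead in two ways. A discrepancy may be reported as a possible allocation fault when there was none, which weakens a sound primary result in a pilot meant to support a full-scale trial proposal. Agreement may be taken as reassurance about allocation, which it cannot give.

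The selection rule also gives up much of the benefit of adjustment. A prognostic variable that happens to balance is left out, and an irrelevant one that happens not to balance goes in. The covariates, the trigger and the reading of the result are all settled after the data are seen.

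**Working it through.** The documents give no alpha, power, effect size, SD or covariate count, so there is no plan figure to reproduce. The check asks what the rule would report if randomization were perfect.

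**Inputs from the documents:** 40 per arm; 1:1 allocation; no balancing on prognostic factors; pre-treatment score in the primary model.

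**Assumptions, not in the documents:** 15 independent baseline variables inspected, jointly explaining 20% of outcome variance; true effect 0.45 SD or zero; two-sided 0.05; 'large' read as a standardized mean difference (SMD) above 0.25, 0.5 or 0.8; 'substantial difference' read as a change of significance verdict; one post-treatment outcome; no dropout.

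**Step 1: chance imbalance.** SE(SMD) = sqrt(2/40) = 0.224. For a cut c, p = P(|SMD| > c) = 2 × (1 − Φ(c/0.224)). For 15 variables, P(at least one) = 1 − (1 − p)^15.

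- c = 0.25: p = 0.264. Expected number = 15 × 0.264 = 3.95. P(at least one) = 0.99.
- c = 0.5: p = 0.025. P(at least one) = 0.32. With the SD estimated from the sample (t, 78 df), this is 0.35.

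At the lower cut, about four imbalanced variables are the norm. At 0.5, about one trial in three has at least one.

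**Step 2: change of verdict.** Trials of 40 v 40 were simulated with correct randomization, at least 2,000 per setting. The primary model was run with and without a baseline score (R² 0.3). The secondary model added every variable beyond the cut. The table gives the share of all trials in which exactly one of the two models had p<0.05.

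| 'Large' means SMD above | True effect 0.45 SD | No true effect |
|---|---|---|
| 0.25 | about 15-19% | about 5% |
| 0.5 | about 5% | 1-2% |
| 0.8 | near 0% | 0% |

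At the 0.5 cut, among trials where a covariate is triggered, the rate is 5%/35% = roughly 14%.

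**Step 3: sensitivity.** With 10 or 15 variables, five of them prognostic, covariate R² 0.1 or 0.3 and effects of 0.4 to 0.5 SD, the verdict changed in 3.0% to 22.3% of all trials (cuts 0.25 and 0.5). With no effect it changed in 0.9% to 5.3%. Changes went both ways. In the setting with 22.3%, the primary result lost significance in 11.0% of trials and gained it in 22.3 − 11.0 = 11.3%. If 'substantial' requires one p-value below 0.05 and the other above 0.10, the rates at 0.45 SD fall to 6-8% (cut 0.25) and about 2% (cut 0.5).

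In the null settings the primary test rejected in 4.3% to 5.4% of trials, so its size held. Randomization never failed in any simulated trial, so each change of verdict that the rule flags is a false alarm.

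**The case against.** The text is hedged: it speaks of substantial differences, a potential problem, and caution. It does not declare the trial invalid, replace the primary result or change a decision rule. Caution is also defensible when the result of an 80-person pilot depends on adjustment. This stands. A reader might infer that the plan would discredit the primary result, but the wording does not go that far. What is wrong is the cause it names for the discrepancy.

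The plan also confines the imbalance-selected covariates to a secondary analysis and pre-specifies the pre-treatment score in the primary model. This stands too. A reader might infer that data-driven selection biases the primary estimate or inflates its type I error. The documents rule that out.

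The rates depend on inputs that the plan does not supply. With a strict meaning of 'large' they almost vanish, so no single percentage can be quoted as the plan's error rate. That limits the size of the problem but does not make a model discrepancy a valid test of allocation.

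Finally, the documents do not show which baseline variables predict the WHOQOL-BREF psychological score. Any list is therefore a judgement for the investigators, to be made before the data are seen.

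**Conclusion.** The point holds as a defect of interpretation. The plan treats disagreement between its primary and imbalance-adjusted analyses as a possible sign of failed randomization, yet correct randomization at 40 per arm produces such disagreement. Under the stated assumptions, and with a true effect of 0.45 SD, the share of trials affected runs from near 0% to about 19%, depending mainly on what 'large' means. With no true effect it is at most about 5%. The logical fault does not depend on these figures.

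The consequence is unwarranted doubt about a sound primary result, or false reassurance when the models agree. The primary estimate, its type I error, the sample size and the conduct of the trial are not affected. This is a cheap improvement to the plan and not a threat to its validity.

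**What to change.** 1. Delete the sentence that reads a discrepancy as randomization failure.
2. Replace the imbalance trigger with a short list of baseline covariates already collected, chosen in advance for expected prognostic value and fitted whatever imbalance is seen. Candidates are baseline ISI, CAPS-5 and AHI, new versus existing PAP, and variables that the plan already names as moderators (sedative-hypnotic use, SEMSA, ESS, PSQI).
3. Report that model beside the primary one as a precision and robustness analysis, comparing estimates and confidence intervals.
4. Judge the integrity of randomization from the allocation list and assignment records.
5. In the same edit, reconcile the description of the primary analyses as unadjusted with the pre-treatment score in the primary model.

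The cost is SAP wording and a few degrees of freedom in a secondary model. No new data are needed.
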